6 STUDY DESIGN

6.1 Summary of Study Design

This is a double-blind, randomized, placebo-controlled study of three oral dose levels of MSDC-0602K. Subjects will be screened for eligibility up to 42 days in advance of randomization (between Days -42 and -1). Subjects will be randomized into 1 of 4 treatment groups based on a stratification criteria of presence Type 2 DM (Yes/No), use of Vitamin E \geq 400 IU (Yes/No), and fibrosis score (F1 or \geq F2) and will receive single daily doses of MSDC-0602K (62.5, 125 or 250 mg), or placebo for one year (360 days). Approximately 380 subjects will be randomized to achieve 85 completed subjects in each of the 4 treatment groups. The number of subjects who have a fibrosis score of F1 will be no greater than 50% of each group in order to best inform the design of the Phase 3 clinical trial.

- Male or female subjects with NASH and fibrosis should have an interpretable liver biopsy within 9 months prior to randomization and at the end of study treatment at Visit 7. Double-blind study drug will be dispensed for daily administration starting at Study Visit 1. Subsequent study visits will occur on Days 30 (1 month), 60 (2 months), 90 (3 months), 180 (6 months), 270 (9 months), 360 (12 months) and a 14-day follow-up visit on Day 374. Subjects will self-administer study drug once daily throughout the treatment period through the Day 360 visit. Site personnel will contact subjects every month to inquire about safety, adverse events and serious adverse events.

Blood samples will be collected for trough level assay of MSDC-0602 and major metabolite MSDC-0597 concentrations. Fasting blood samples will also be collected for analysis of

biomarkers and for safety chemistry/hematology laboratory testing at all outpatient visits. Urine samples will be collected for urinalysis quarterly throughout the study.

Subjects will return to the clinic for a Follow-Up visit approximately 2 weeks after the final dose (Day 374, Visit 8) for blood sampling. A complete physical examination will be performed at Screening and at the Follow-up visit on Day 374, and a limited physical examination will be performed at all other study visits.

6.1.1 Schedule of Activities

A schedule of activities is provided in Table 1.

Table 1. Schedule of Activities

Visit Number Study Months Study Day Window	Screen ¹	Treatment							Follow-up
		1	2	3	4	5	6	7	8
		Randomization	1	2	3	6	9	12	
		-42 to -1	1	30	60	90	180	270	360
		N/A	± 7 days						± 3 days
General Activities									
Informed Consent	X								
Medical History	X								
Complete Physical Examination ²	X								X
Limited Physical Examination ²		X	X	X	X	X	X	X	
Vital signs ³	X	X	X	X	X	X	X	X	X
12-lead ECG	X					X		X	X
Pregnancy test (females only)	X	X							X
FSH (post-menopausal females only)	X								
FibroScan ⁴	X							X	
Liver Biopsy ⁵	X							X	
Randomization		X							
Dietary guidance and assessment of alcohol intake ⁶	X	X	X	X	X	X	X	X	
Adverse event review	X	X	X	X	X	X	X	X	X
Concomitant medication review	X	X	X	X	X	X	X	X	
Monthly phone assessment ⁷					X	X	X		
Study drug dispensing ⁸		X			X	X	X		
Central Lab Evaluations									
Hematology & serum chemistry ^{9, 10}	X	X	X	X	X	X	X	X	X
Liver function tests	X	X	X	X	X	X	X	X	
Urinalysis	X	X			X	X	X	X	X
HMW adiponectin, hsCRP, CK-18 [M30 & M65], osteocalcin, and CTX		X				X		X	
Fibrosure, ELF score, APRI, FIB-4 index, Pro-C3		X				X		X	
Serum sample for NMR analysis		X						X	
Blood sample for genotyping analyses (optional) ¹¹		X							
Plasma samples for future miRNA and biomarker testing ¹²		X				X		X	
Trough PK sample ¹³			X		X	X	X	X	

1. ICF may be obtained before the 42-day screening window. Re-testing is allowed within the 42-day Screening period if, in the opinion of the Investigator, the subject may become eligible upon repeat testing
2. Height and body weight are collected at Screening only; body weight, waist circumference measured midway between the lowest rib and the iliac crest, and signs of peripheral edema are collected at all study visits.
3. Vital sign measurements including seated BP and heart rate are collected at every visit; oral temperature is collected at screening, pre-dose on Day 1 and Visit 8.
4. FibroScan is required within 90 days prior to or during Screening.
5. A qualifying liver biopsy is required within 9 months prior to Screening. If a historical liver biopsy result is not available within this period, a liver biopsy must be performed during Screening for eligible subjects who meet all other entry criteria. A liver biopsy is also performed at Visit 7.
6. Non-diabetic subjects are provided the NCEP dietary guidance at Screening and diabetic subjects are provided the ADA dietary guidance at Screening. Guidance regarding alcohol consumption is also provided to all subjects at Screening. All subjects are assessed for compliance with dietary guidelines and alcohol consumption at each visit.
7. Study staff will contact the subjects by phone every month between Visits 4-7 to inquire about adverse events and serious adverse events.
8. 3 bottles dispensed at Visits 1, 4, 5, and 6.
9. Minimum 10-hour fasting blood sample collected pre-dose.
10. FPG and HbA1c will also be measured at Visits 1, 5 and 7.
11. A separate genotyping informed consent is required to enable collection of blood sample for genotyping analyses.
12. At each timepoint, plasma samples will be split into two separate vials and stored for biomarker testing, including miRNA, to be determined at a later date.
13. Pre-dose trough PK sample collected for analysis of MSDC-0602 and MSDC-0597.

6.2 Study Activities

6.2.1 Method of Assigning Subjects to Treatment

Subjects who meet all of the inclusion criteria and none of the exclusion criteria will be allocated centrally by an IXRS to one of the four treatment groups in a 1:1:1:1 allocation ratio, according to a central randomization scheme stratified by the presence of T2DM (Yes/No), use of Vitamin E \geq 400 IU (Yes/No), and fibrosis score (F1 or \geq F2), each enrolled subject will be sequentially assigned the next available randomization number and be allotted the specified treatment corresponding to that randomization number.

6.2.2 Screening Period (Days -42 to -1)

Prior to conducting any study-related procedures, written informed consent must be obtained from the subject. Participation in this study is voluntary. The nature of the study will be fully explained to each subject during the informed consent process and the subject will have the opportunity to ask questions. An informed consent document will then be signed by the subject and the person performing the consent discussion, and retained by the Investigator. A copy of the informed consent form will be given to the subject. Informed consent may be obtained before the 42-day screening window.

After obtaining a signed informed consent form, study site personnel will access the IXRS to assign a subject identification (ID) number to a potential study subject. This number will be used to identify the patient for the remainder of the study. Screening evaluations to determine subject eligibility will be conducted within 42 days prior to randomization (Day 1) in the study. Subjects must fast for at least 10 hours prior to the following Screening procedures.

- Medical history
- Complete physical examination
- Vital sign measurements
- 12-lead ECG
- Pregnancy test (serum, females only)
- FSH (post-menopausal females only)
- Transient elastography measure of liver fibrosis (FibroScan) within 90 days prior to or during Screening
- Qualifying liver biopsy within 9 months prior to Screening. If a usable liver biopsy is not available, a liver biopsy must be performed during Screening for eligible subjects who meet all other entry criteria after the following criteria are confirmed:
 - a. AST \geq 20 U/L
 - b. FibroScan with CAP score \geq 270 db/m and kPa \geq 8.5
- Documentation of any AEs
- Assessment of alcohol use

- Provide and discuss the recommended standard of care diet program, the NCEP step 1 diet for subjects who are not diabetic and the ADA diet recommended for subjects with diabetes ([Appendix 2 and Appendix 1](#))
- Clinical chemistry and hematology laboratory evaluations
- Liver function tests
- Urine sample for urinalysis
- Concomitant medication review

Re-testing is allowed within the 42-day Screening period if, in the opinion of the Investigator, the subject may become eligible upon repeat testing.

Eligible subjects will be scheduled to return to the clinic for the start of the 12-month treatment period. Male subjects will be advised to inform female partners of their participation in the study and to use adequate contraceptive methods (including a condom plus another form of contraception) if engaging in sexual intercourse with a woman who could become pregnant.

6.2.3 Study Visit 1

Day 1 is the day of randomization, which is usually the day of the first dose of randomized study drug treatment.

Continued eligibility based on exclusion criteria relating to safety and concomitant medications will be reassessed. Eligible subjects will be instructed to report to the clinic for a study visit on Day 1 following a minimum 10-hour fast. The following procedures will be performed for all subjects at Study Visit 1 (Day 1):

- Limited physical examination
- Vital sign measurements
- Pregnancy test (dip-stick, females only)
- Randomization
- Assess compliance to diet (Y/N) and alcohol intake (Y/N)
- Clinical chemistry and hematology laboratory evaluations
- Liver function tests
- HMW adiponectin, hsCRP, and CK-18 [M30 & M65], osteocalcin and serum CTX
- Calculation of Fibrosure, APRI, FIB-4 index, ELF score and its individual components (TIMP-1, PIIINP and HA), and Pro-C3
- NMR analysis of lipoprotein particle size
- Genotyping analyses (provided subject has signed the ancillary informed consent for genotype testing, which is optional)
- Future miRNA and additional biomarkers of interest testing

- Urine sample for urinalysis
- Documentation of any AEs
- Notation of any change in concomitant medication use
- Study drug (3 bottles of 33 capsules from the assigned kit) will be dispensed

6.2.4 Study Visit 2, Month 1

Subjects will be instructed to report to the clinic for a study visit on Day 30 following a minimum 10-hour fast and without having taken their morning dose of study drug. The following procedures will be performed for all subjects at Study Visit 2 (Day 30 ± 7 days):

- Limited physical examination
- Vital sign measurements
- Assess compliance to diet (Y/N) and alcohol intake (Y/N)
- Clinical chemistry and hematology laboratory evaluations
- Liver function tests
- Trough PK analysis of MSDC-0602 and MSDC-0597
- Notation of any change in concomitant medication use
- Documentation of any AEs

6.2.5 Study Visit 3, Month 2

Subjects will be instructed to report to the clinic on Day 60 following a minimum 10-hour fast and without having taken their morning dose of study drug. The following procedures will be performed for all subjects at Study Visit 3 (Day 60 ± 7 days):

- Limited physical examination
- Vital sign measurements
- Assess compliance to diet (Y/N) and alcohol intake (Y/N)
- Clinical chemistry and hematology laboratory testing evaluations
- Liver function tests
- Documentation of any AEs
- Notation of any change in concomitant medication use

6.2.6 Study Visit 4, Month 3

Subjects will be instructed to report to the clinic on Day 90 following a minimum 10-hour fast and without having taken their morning dose of study drug. Subjects should return the unused study drug. The following procedures will be performed for all subjects at Study Visit 2 (Day 90 ± 7 days):

- Limited physical examination
- Vital sign measurements
- Assess compliance to diet (Y/N) and alcohol intake (Y/N)
- Clinical chemistry and hematology laboratory evaluations
- Liver function tests
- Urine sample for urinalysis
- Trough PK analysis of MSDC-0602 and MSDC-0597
- Documentation of any AEs
- Notation of any change in concomitant medication use
- Monthly phone calls to inquire about adverse events and serious adverse events
- Study drug (3 bottles of 33 capsules from the assigned kits) will be dispensed

6.2.7 Study Visit 5, Month 6

Subjects will be instructed to report to the CPRU for an outpatient study visit on the morning of Day 180 following a minimum 10-hour fast and without having taken their morning dose of study drug. Subjects should return the unused study drug. The following procedures will be performed for all subjects at Study Visit 5 (Day 180 \pm 7 days):

- Limited physical examination
- Vital sign measurements
- 12-lead ECG
- Assess compliance to diet (Y/N) and alcohol intake (Y/N)
- Clinical chemistry and hematology laboratory evaluations
- Liver function tests
- Urine sample for urinalysis
- HMW adiponectin, hsCRP, and CK-18 [M30 & M65], osteocalcin and serum CTX
- Calculation of Fibrosure, APRI, FIB-4 index, ELF score and its individual components (TIMP-1, PIIINP and HA), and Pro-C3
- Future miRNA and additional biomarkers of interest testing
- Trough PK analysis of MSDC-0602 and MSDC-0597
- Notation of any change in concomitant medication use
- Documentation of any AEs
- Monthly phone calls to inquire about adverse events and serious adverse events
- Study drug (3 bottles of 33 capsules from the assigned kits) will be dispensed

6.2.8 Study Visit 6, Month 9

Subjects will be instructed to report to the clinic on the morning of Day 270 following a minimum 10-hour fast and without having taken their morning dose of study drug. Subjects should return the unused study drug. The following procedures will be performed for all subjects at Study Visit 6 (Day 270 \pm 7 days):

- Limited physical examination
- Vital sign measurements
- Assess compliance to diet (Y/N) and alcohol intake (Y/N)
- Blood sample for clinical chemistry and hematology laboratory testing
- Liver function tests
- Blood sample for trough PK analysis of MSDC-0602 and MSDC-0597
- Urine sample for urinalysis
- Monthly phone calls to inquire about adverse events and serious adverse events
- Notation of any change in concomitant medication use
- Documentation of any AEs
- Study drug (3 bottles of 33 capsules from the assigned kits) will be dispensed

6.2.9 Study Visit 7, Month 12

Subjects will be instructed to report to the clinic on the morning of Day 360 following a minimum 10-hour fast before taking their morning dose of study drug. Subjects should return the unused study drug. The following procedures will be performed for all subjects at Study Visit 7 (Day 360 \pm 7 days):

- Limited physical examination
- Vital sign measurements
- 12-lead ECG
- Assess compliance to diet (Y/N) and alcohol intake (Y/N)
- Transient elastography of liver fibrosis (FibroScan)
- Liver biopsy
- Clinical chemistry and hematology laboratory testing
- Liver function tests
- Urine sample for urinalysis
- HMW adiponectin, hsCRP, CK-18 [M30 & M65], osteocalcin and serum CTX

- Calculation of Fibrosure, ELF score, and its individual components (HA, PIIINP, TIMP-1), APRI, FIB-4 index, and Pro-C3
- NMR analysis of lipoprotein particle size
- Future miRNA and additional biomarkers of interest testing
- Trough PK analysis of MSDC-0602 and MSDC-0597
- Notation of any change in concomitant medication use
- Documentation of any AEs

6.2.10 Study Visit 8, Day 374 (Follow-Up Visit)

The following procedures will be performed for all subjects at the Follow-Up Visit (Study Visit 8, Day 374 \pm 3 days):

- Complete physical examination
- Vital sign measurements
- 12-lead ECG
- Pregnancy Test (females only)
- Clinical chemistry and hematology laboratory evaluations
- Urine sample for urinalysis
- Documentation of any AEs

6.2.11 Additional Follow-Up Visits

In the event of an AE that has not resolved by the follow-up visit, additional follow-up visits may be scheduled until the event resolves or is deemed to be a permanently continuing event. At the Investigator's discretion, minor AEs may be followed until resolution via a telephone contact.

6.3 Discontinuation of Study Drug and Study Termination

Subjects are free to discontinue participation in the study at any time and for any reason without prejudice to future medical care; however, prior to randomization, it should be made clear to potential subjects that early withdrawal from the study including loss to follow up can be extremely damaging to the scientific research and may pose some risk to the subject. If a subject withdraws consent to be treated with study drug prior to receiving any dose of study drug, the subject should be discontinued from the study. Once a subject has been randomized, the investigator will make every reasonable effort to keep the subject in the study.

Subjects may withdraw from study for the following reasons:

- Withdrawal of informed consent: A subject should be considered to have withdrawn consent when the subject no longer wishes to participate in any aspect of the study, and

does not want any further assessments, visits, or contact. A subject's refusal to participate in specific aspects of the study, such as a refusal to continue taking study drug or to provide blood samples, will NOT constitute withdrawal of consent. Investigators should make every effort to facilitate the subject's continued participation in remaining aspects of the study.

- Subject is lost to follow-up: A subject will not be considered lost to follow-up until just prior to database lock and after all efforts to contact the subject have been exhausted.

If a subject withdraws from study for any reason above, vital status as of Day 374 may be obtained through public registries as permitted by local regulations.

Subjects who wish to withdraw consent from the study, to the extent possible, will undergo an End of Study evaluation equivalent to Visit 8 (Day 374) (see Table 1).

The appropriate case report forms (eCRFs) should be completed, including an explanation as to why the subject participation in the study is being discontinued. Subjects who do not complete the study will not be replaced.

The Investigator and Cirius Therapeutics, Inc. have the right to discontinue study drug dosing from any subject in the event of an intercurrent illness, AE, protocol violation, or other reason including, but not limited to:

- Need for any treatment not allowed by the protocol
- Subject's inability to comply with protocol-specified procedures
- Sites with serious GCP or quality concerns
- Adverse event that in the opinion of the Investigator requires discontinuation of study drug
- Development of symptoms of CHF that in the opinion of the Investigator requires immediate treatment.

6.4 Type 2 Diabetes Mellitus

Refer to subject's healthcare provider for diabetic care; however, note that no change in dose is allowed for GLP1 agonists or SGLT2 inhibitors during the study and these drugs cannot be added as rescue medications during the study if the subject had not been on a previous stable dose of either drug 3 months prior to randomization. Use of PPAR γ agonists (pioglitazone or rosiglitazone) or insulin are prohibited during the study.

Subjects being treated with therapeutic agents for diabetes should be on stable dose(s) of the following antidiabetic medications at least 3 months prior to randomization and for the full duration of the trial: metformin, GLP1 agonists, SGLT2 inhibitors, sulfonylureas and DPP4 inhibitors.

If, during the study, a measurement of HbA1c exceeds 9.5% at two consecutive visits, the following suggested rescue approach may be followed:

1. Start metformin or up-titrate metformin if the subject is already taking it

2. Start a DPP4 inhibitor or uptitrate the DPP4 inhibitor if the subject is already taking a DPP4 inhibitor
3. Start careful titration of a sulfonylurea or titrate sulfonylurea if the subject is already taking it.

If no reversible cause is identified or hyperglycemia persists despite counseling and all permitted co-therapies, subject should be discontinued from study drug, referred for treatment, and continue in the study and complete the required study visits.

If a measurement of fasting plasma glucose (FPG) during the study is lower than 60 mg/dL, an alert will be sent to the investigational site and confirmatory FPG should be performed at the site within 7 days. In case of a symptomatic hypoglycemic event and if the subject is on a sulfonylurea, the sulfonylurea dose should be reduced by 50% or discontinued. Severe hypoglycemia is defined as any hypoglycemia requiring the assistance of a third party, hospitalization or associated with seizures or coma. Refer to [Section 9](#) Adverse Events for reporting instructions.

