7.4 Laboratory Assessments

For all subjects, blood samples for safety laboratory assessments will be drawn at every visit (Table 1). All blood samples for clinical chemistry and hematology should be drawn in a fasted state (approximately 10 hours). A certified central clinical laboratory will be used to perform all routine hematology, clinical chemistry and urinalysis. Table 2 provides a summary of safety laboratory tests performed during the study.

All clinical laboratory tests will be performed by the central laboratory specified in Form FDA 1572 Section 4. The central laboratory reference ranges will be used. Eligibility at screening will be based on central laboratory assessments.

Local laboratory assessments may be used to manage patient care during the conduct of the study (eg, routine care, unscheduled visits, urgent care). Such laboratory data will not be entered into the study database and local laboratories will not be included on the FDA 1572 form.

Table 2. Safety Laboratory Tests

Hematology	Chemistry	Urinalysis	Other
Hemoglobin	Albumin	Bilirubin, Blood	
Hematocrit	Alkaline phosphatase	Glucose, Ketones, pH, creatinine,	
Platelets, RBC with indices	ALT, AST, BUN, Bicarbonate	Protein, Specific gravity	Pregnancy test ^{b,c} FSH ^{b,c}
WBC with differential	Calcium, Chloride, Creatinine, Fasting Plasma Glucose, Fasting Insulin, FFA	Microscopic exam ^a	hsCRP CK-18 [M30 & M65] HMW adiponectin osteocalcin Serum CTX TIMP-1 PIIINP HA Pro-C3
HbA1c	LDH, Phosphorus		
INR, PT	Potassium, Sodium Gamma-glutamyl transpeptidase Total Bilirubin Total Protein, Uric acid Cholesterol (total, HDL, LDL, VLDL) Triglycerides		

^a Only if positive for blood or protein

^b Only at Screening (β-hCG), Day 1 (urine dipstick), and Day 374 (urine dipstick)

^c Females only.

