7.5 Efficacy and Pharmacokinetic Assessments

For all subjects, blood samples for pharmacologic (efficacy and safety) assessments will be drawn at all visits except Screening (Table 1). All blood samples should be drawn in a fasted state (approximately 10 hours). Instructions for collecting, processing, storing and shipping of blood samples for pharmacologic and pharmacokinetic analyses will be provided in the Laboratory Manual.

Blood samples for trough PK analysis of MSDC-0602 and MSDC-0597 will be collected pre-dose at Study Visits 2, 4, 5, 6 and 7 (Days 30, 90, 180, 270 and 360).

Blood samples for analysis of FPG and HbA1c will be collected at Screening.

Blood samples for analysis of insulin, HOMA-IR, FPG, HbA1c, TG, FFA and fasting cholesterol (total, HDL, LDL, VLDL) will be collected as part of the standard chemistry profile at Study Visits 1, 5, and 7 (Days 1, 180 and 360).

Blood samples for analysis of liver function tests (AST, ALT, bilirubin, PT/INR, ALP, GGT and albumin) will be collected at Study Visits 1, 2, 3, 4, 5, 6 and 7 (Days 1, 30, 60, 90, 180, 270 and 360).

Blood samples for analysis of HMW adiponectin, hsCRP, osteocalcin, serum CTX concentrations will be collected at Study Visits 1, 5, and 7 (Days 1, 180, and 360).

Blood samples for biomarkers of liver apoptosis (CK-18 [M30 and M65]) will be collected at Visits 1, 5 and 7 (Days 1, 180, and 360), whereas blood samples for TIMP-1, PIIINP, HA will be collected at Visits 1 and 7 (Days 1 and 360).

Serum samples for NMR analysis of lipoprotein particle size will be collected at Study Visits 1 and 7 (Days 1 and 360).

Blood samples will be collected at Visit 1 (Day 1) to be analyzed for genotyping.

Plasma samples for future miRNA measurements and additional biomarkers of interest will be collected at Study Visits 1, 5 and 7 (Days 1, 180 and 360).

Data obtained from the circulating liver function tests and other biomarkers will be used to calculate composite scores that may provide an indirect measure of changes in fibrosis from baseline to the 12 month endpoint (Days 1 and 360).

It is estimated that approximately 226 mL of blood for the safety, pharmacokinetic, and pharmacodynamic parameters will be drawn from each subject who completes the trial.

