7.8 Concomitant Medications and Other Therapy

For diabetic subjects, use of any diabetic medication other than metformin (generic or Glucophage®), GLP-1 agonists, SGLT2 inhibitors, sulfonylureas or DPP4 inhibitors 3 months prior to the diagnostic liver biopsy or during the study is prohibited. Subjects on metformin, GLP1 agonists, SGLT2 inhibitors, sulfonylureas or DPP4 inhibitors must have been stabilized on their current dose for a period of 3 months prior to diagnostic liver biopsy and the doses should not be altered during the study except as provided in the rescue medication instructions ([Section 6.4](#)).

Use of other prescription or over-the-counter (OTC) medications or herbal remedies is allowed during the study, as long as the subject has been stabilized on a dose for 6 weeks prior to study entry. Antiaggregants are allowed but should be discontinued for at least 5 days prior to the liver biopsy. Any concomitant medication taken during the study must be recorded in the eCRF.

Use of ursodeoxycholic acid is prohibited as there is insufficient knowledge of its effects in this subject population.

MSDC-0602K is metabolized to its hydroxymetabolite by a carbonyl reductase. This is a ubiquitous enzyme and there is no prior evidence to indicate that any concomitant medications would interfere with this metabolism. There is minimal interaction of MSDC-0602K or its metabolite with CYP P450 systems, either by direct inhibition or induction. However, there is a potential for inhibition of CYP2C8 and CYP2C9 particularly with the active metabolite, which is the predominant moiety in circulation. For these reasons, the following medications are also prohibited in this trial: paclitaxel, phenytoin, warfarin, celecoxib, tolbutamide and repaglinide.

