Changes in HbA1c will also be evaluated with shift tables presenting movement in and out of reference ranges from baseline to 6 and to 12 months. These shift tables will be presented in (1) subjects without T2DM, (2) subjects with T2DM, and (3) subjects with T2DM without major changes in glycemetic control medications. The HbA1c “normal range” will be considered 4.0-5.6% in subjects without T2DM and 5.7-6.4% in subjects with T2DM.

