7.9.2 Laboratory Evaluations

Values for the following safety laboratory tests (hematology, serum chemistry, and urinalysis) will be listed and summarized by treatment group and visit.

Hematology	Serum Chemistry	Urinalysis
Hemoglobin	Albumin*	Bilirubin
Hematocrit	Alkaline phosphatase (ALP)*	Blood
Platelets, RBC with indices	Alanine aminotransferase (ALT)*	Glucose
WBC with differential	Aspartate Aminotransferase (AST)*	Ketones
HbA1c*	Blood Urea Nitrogen (BUN)	pH
INR*	Bicarbonate	Creatinine
PT*	Calcium	Protein
	Chloride	Specific gravity
	Creatinine	Microscopic exam (if blood or protein positive)
	Fasting plasma glucose (FPG)*	
	Fasting insulin*	
	Free fatty acid (FFA)*	
	Lactate dehydrogenase (LDH)	
	Phosphorus	
	Potassium	
	Sodium	
	Gamma-Glutamyl transpeptidase (GGT)*	
	Total Bilirubin*	
	Total protein	
	Uric acid	
	Cholesterol (total, HDL, LDL, VLDL)*	
	Triglycerides*	

*Also considered an efficacy parameter.

All laboratory data will be reported in International System of Units (SI).

For analysis purposes, values preceded by a “<” or a “>” sign (i.e., those below or above the limits of quantification) will be considered equal to 0.5 × the lower limit or 1.5 × the upper limit of quantification, respectively. The proportion of subjects with values below the lower limit and above the upper limits of quantification will be provided among the summary statistics.

Laboratory evaluations measured on a continuous scale will be summarized by visit using standard descriptive statistics for the SAF population. Changes from baseline will also be summarized. Summaries will be presented for log-transformed values of ALT, AST, ALP, and GGT, in addition to summaries of non-transformed values. For analysis by visit, analysis windowing as described in Section 6.1 will be used for each scheduled visit such that unscheduled visits will also be considered. For each laboratory analyte, the baseline value will be defined as last scheduled or unscheduled value collected prior to the first dose of treatment.

For hematology and serum chemistry, shift tables presenting movement in and out of reference range from baseline to each scheduled post-baseline visit will be provided for each treatment group. An additional shift table will be produced for ALT where the upper normal limit is defined as 19 U/L for women and 30 U/L for men. Corresponding shift tables (normal vs. high /

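### The HbA1c rescue trigger in Protocol 6.4 needs two consecutive high visits, but a subject at or below 9.5% on Day 1 has only one scheduled HbA1c before Day 360

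*Protocol*

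**What the plan says.** **The rule.** Protocol Section 6.4: "If, during the study, a measurement of HbA1c exceeds 9.5% at two consecutive visits, the following suggested rescue approach may be followed". The steps that follow are to start or raise metformin, a DPP4 inhibitor or a sulfonylurea. Outside those steps background therapy is held fixed. Section 7.8 says of the permitted agents that "the doses should not be altered during the study except as provided in the rescue medication instructions". Section 6.4 also freezes GLP-1 agonist and SGLT2 inhibitor doses and bars insulin and PPARγ agonists.

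**The explicit schedule.** Table 1 footnote 10: "FPG and HbA1c will also be measured at Visits 1, 5 and 7". Protocol Section 7.5 names the same three visits (Days 1, 180 and 360) and adds Screening. The SAP is consistent with this: Section 7.8.4 plans HbA1c "shift tables presenting movement in and out of reference ranges from baseline to 6 and to 12 months".

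**End of dosing.** Protocol Section 6.1: "Subjects will self-administer study drug once daily throughout the treatment period through the Day 360 visit".

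**Text that points to more frequent testing.** Protocol Section 7.4 says that "blood samples for safety laboratory assessments will be drawn at every visit", and Table 2 puts HbA1c in its hematology column. SAP Section 7.9.2 also lists HbA1c under hematology and says: "Values for the following safety laboratory tests (hematology, serum chemistry, and urinalysis) will be listed and summarized by treatment group and visit".

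**Repeats ordered elsewhere.** Raised liver tests (Section 6.5) and PT/INR (Section 6.6) are to be repeated within about 48 to 72 hours, and a fasting glucose below 60 mg/dL within 7 days (Section 6.4). Section 6.4 orders no repeat after a high HbA1c.

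**The concern.** A rule that needs two consecutive high values works only if there are enough measurements during treatment to supply them. On the explicit schedule there is one HbA1c between the first and last treatment visits. For a subject who starts at or below 9.5%, the second value arrives at the visit where study drug stops, too late for rescue during treatment.

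The rule is also the stated route by which doses of metformin, a DPP4 inhibitor or a sulfonylurea already in use may be raised. Whether a new permitted class may be started before the trigger is met is ambiguous. The SAP attaches some consequence to this: prohibited changes in diabetes therapy may lead to exclusion from the per-protocol set (Section 5.4.1), and disallowed dose changes are tabulated as prohibited medication (Section 7.6). Whether a dose increase at, say, Day 200 is permitted rescue or a deviation depends on a trigger that the schedule leaves unclear.

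**Working it through.** The plan gives no figure to reproduce here. The check enumerates visits.

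**Inputs.** Visit days 1, 30, 60, 90, 180, 270 and 360, each after Day 1 with a ±7-day window (Table 1). Trigger: above 9.5% at two consecutive visits (Section 6.4). Dosing ends at the Day 360 visit (Section 6.1). HbA1c at Screening and Days 1, 180 and 360 (footnote 10, Section 7.5). 380 subjects randomized (Section 11.1). Unscheduled-visit windows from SAP Section 6.1.

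**Step 1: what consecutive visits can mean on the explicit schedule.** As adjacent study visits, the only pair with HbA1c at both is Screening and Visit 1, both before treatment. As consecutive HbA1c visits, two pairs reach into treatment: Visits 1 and 5 (met at Day 180) and Visits 5 and 7 (met at Day 360). The second, more workable meaning is used below.

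**Step 2: subject at or below 9.5% on Day 1.** Only Visits 5 and 7 remain.

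- Nominal gap: 360 − 180 = 180 days.
- Range with windows: 353 − 187 = 166 to 367 − 173 = 194 days.
- Dosing days left when met: 360 − 360 = 0.

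**Step 3: subject above 9.5% on Day 1 and Day 180.** Met at Day 180, with 360 − 180 = 180 dosing days left. This can happen: Screening may precede Day 1 by up to 42 days, and Section 6.2.3 rechecks only exclusion criteria on Day 1, whereas the HbA1c limit is inclusion criterion 5.

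**Step 4: comparison for a first high value at Day 180, with Day 1 at or below 9.5%.**

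| Schedule | Scheduled HbA1c strictly between Day 1 and Day 360 | Trigger met | Dosing days left |
|---|---|---|---|
| Footnote 10 and Section 7.5 | 1 (Day 180) | Day 360 | 0 |
| Every visit (Table 2 read broadly) | 5 (Days 30, 60, 90, 180, 270) | Day 270 | 360 − 270 = 90 |
| Days 1, 90, 180, 270, 360 with a repeat within 28 days (assumed) | 3 (Days 90, 180, 270) | by Day 180 + 28 = 208 | 360 − 208 = 152 |

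Under the last row, first high values at Days 90 and 270 would be confirmed by Days 118 and 298, leaving 242 and 62 dosing days.

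**Step 5: would a 28-day repeat disturb the SAP windows?** Take the SAP Section 6.1 column for parameters measured at all visits except 2, 3 and 8. The latest repeats are 97 + 28 = 125 (window ends 135), 187 + 28 = 215 (ends 225) and 277 + 28 = 305 (ends 315). All stay within the visit's own window, where SAP 6.1 prefers the scheduled value. Up to 38 days would fit. A repeat after Visit 1 would not: Days 2 to 29 fall in the Month 3 window (Days 2 to 135), so the repeat rule should be post-baseline only.

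**Step 6: assays.** 2 added visits × 380 subjects = 760 at most.

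**The case against.** **Table 2 and SAP 7.9.2 settle the schedule as every visit, so the rule works.** This is a weak inference. Table 2 has no visit column and also lists tests tied elsewhere to particular visits, such as fasting insulin, FFA, lipids and hsCRP. In SAP 7.9.2, a summary by visit can mean the visits at which a test is done, and SAP 6.1 has a window column for Visits 1, 5 and 7. Footnote 10 and Section 7.5 are the more specific text. For the same reason, a reader who infers a flat contradiction between two stated schedules goes too far. The documents leave a doubt, which covers fasting glucose as well, and the Laboratory Manual that might resolve it is not among them.

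**Glycemic cover exists without this rule.** This stands. The rescue steps are suggested and optional. Section 6.4 refers diabetic care to the subject's own provider. Section 7.4 lets local laboratory tests guide care, although those results stay out of the study database. Investigators review out-of-range central results (Section 13.2), and study drug can be stopped if a disallowed treatment is needed (Section 6.3). Unscheduled visits are possible, and Section 6.4 does not say that the HbA1c must be central. What remains is that nothing orders a repeat, and Section 7.8 limits what the provider may change until the trigger is met.

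**The stop sentence in Section 6.4 is sound.** It joins the absence of a reversible cause and persistent hyperglycemia with *or*, so read literally it permits stopping before rescue has been tried. The phrase on counseling and co-therapies can be read as covering both limbs. This is a separate, optional wording point.

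**Conclusion.** The point holds as a minor defect in the rescue rule. On scheduled draws, a subject at or below 9.5% on Day 1 cannot meet the trigger before Day 360, when no dosing days remain. The same subject would trigger at Day 270 if HbA1c were drawn at every visit, or by Day 208 with a 28-day repeat. These figures use nominal visit days and take consecutive visits to mean consecutive HbA1c visits.

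Three stronger inferences are not supported:

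- That the rule can act only as dosing ends for everyone. A subject above 9.5% on both Day 1 and Day 180 could trigger at Day 180.
- That subjects with diabetes lack glycemic safety cover. The routes listed above remain open.
- That the efficacy result is at risk. The primary mITT analysis does not use HbA1c or the rescue rule.

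The documents do not give the number of subjects affected, and no estimate is made.

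**What to change.** 1. **Trigger.** If HbA1c exceeds 9.5% at any post-baseline visit before Visit 7, alert the site and repeat HbA1c within a set interval. If the repeat also exceeds 9.5%, the rescue steps may begin. The 28 days used here is an assumption; the documents give no interval for HbA1c.
2. **Schedule.** Add HbA1c at Visits 4 and 6 (Days 90 and 270), where blood is already drawn. State one schedule for HbA1c and fasting glucose in Table 1 footnote 10, Protocol Section 7.5, Table 2 and SAP Section 7.9.2. In SAP Section 6.1, HbA1c then moves to the column for parameters measured at all visits except 2, 3 and 8.
3. **Optional wording.** Make the stopping condition hyperglycemia that persists after counseling, correction of any reversible cause and all permitted co-therapies. Keep the rest of the sentence: stop study drug, refer for treatment, and stay in the study for the remaining visits.

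**Cost.** One short protocol amendment with a matching SAP edit, at most 760 extra assays with no added scheduled visits, and one repeat draw per high value. For unscheduled HbA1c values, the Month 6 window narrows from Days 2–270 to Days 136–225, and the Month 12 window from Day 271 onward to Day 316 onward.

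The SAP is dated May 2019, and its Section 8 already describes data cleaning, so conduct may be well advanced. If visits are complete the protocol can no longer be changed, and the study report should state which HbA1c schedule was run.
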